## **4.2 METHOD OF TREATMENT ASSIGNMENT**

This is an observational study; all patients will be assigned to the treatment group.

## **4.3 STUDY TREATMENT**

The investigational medicinal product (IMP) for this study is Xofluza.

### **4.3.1 Study Treatment Formulation, Packaging, and Handling**

#### **4.3.1.1 Xofluza**

Xofluza will be supplied by the Sponsor as tablets.

For information on the formulation and handling of Xofluza, see the Xofluza Investigator's Brochure.

### **4.3.2 Study Treatment Dosage, Administration, and Compliance**

The treatment regimens are summarized in Section 3.1.

The study treatment will be administered by a certified prescribing provider at mobile testing sites.

Any overdose or incorrect administration of Xofluza should be noted in the patient's medical records and reported according to Section 5.5 (Special Situations Reports). Adverse events associated with an overdose or incorrect administration of any of the study treatments should be recorded in the patient's medical records.

#### **4.3.2.1 Xofluza**

The treatment regimens are summarized in Section 3.1.

Xofluza will be administered orally according to body weight (40 mg for patients weighing 20 to < 80 kg; 80 mg for patients weighing  $\geq$  80 kg) either in tablet form (20 mg or 40 mg tablets).

## **4.4 CONCOMITANT THERAPY**

Concomitant therapy consists of any medication (e.g., prescription drugs, over-the-counter drugs, vaccines, herbal or homeopathic remedies, nutritional supplements) used by a patient in addition to protocol-mandated treatment from 7 days prior to the study visit. All such medications should be reported to the investigator and recorded in the patient's medical records.

### **4.4.1 Permitted Therapy**

All therapies required for the management of the patient's acute illness are permitted except for those listed below in Section 4.4.3 (Prohibited Therapy).

#### **4.4.2        Cautionary Therapy**

Polyvalent cation-containing products may decrease plasma concentrations of Xofluza. Thus, dairy products, calcium-fortified beverages, polyvalent cation-containing oral laxatives or oral antacids, and oral supplements containing iron, zinc, selenium, calcium, or magnesium should not be taken with Xofluza, where possible. Live attenuated influenza vaccines may be affected by antivirals.

#### **4.4.3        Prohibited Therapy**

Use of the following concomitant therapies is prohibited as described below:

- Investigational therapy (other than the protocol-mandated study treatment) is prohibited within 5 half-lives or 30 days (whichever is longer) prior to initiation of study treatment and during the study
- Influenza antiviral drugs (peramivir, laninamivir, oseltamivir, zanamivir, rimantadine, umifenovir or amantadine)
- Immunosuppressants (including biologics)
- Investigational therapy (other than protocol-mandated study treatment)
- Concomitant use of herbal therapies is prohibited as their pharmacokinetics, safety profiles, and potential drug-drug interactions are generally unknown

### **4.5            STUDY ASSESSMENTS**

The schedule of activities to be performed during the study is provided in Appendix 1. All activities must be performed and documented for each patient. Patients will be closely monitored for safety and tolerability throughout the study. Patients should be assessed for toxicity prior to each dose; dosing will occur only if the clinical assessment and local laboratory test values are acceptable.

At applicable sites, certain study assessments may be performed by certified prescribing pharmacist (CPP) professional at the mobile testing location. The Investigator will ensure that all CPPs are licensed, qualified, and in good standing, as per applicable regulations, and that appropriate background checks have been performed.

#### **4.5.1        Informed Consent Forms and Screening Log**

Written informed consent for participation in the study must be obtained before performing any study-related procedures (including screening evaluations). Informed Consent Forms for enrolled patients and for patients who are not subsequently enrolled will be maintained at the study site.

All screening evaluations must be completed and reviewed to confirm that patients meet all eligibility criteria before enrollment. The investigator will

maintain a screening log to record details of all patients screened and to confirm eligibility or record reasons for screening failure, as applicable.

#### **4.5.2 Medical History, Concomitant Medication, and Demographic Data**

Medical history, including clinically significant diseases, surgeries, cancer history (including prior cancer therapies, current cancer stage, and procedures), menstrual history, fertility history, and puberty history, will be recorded. In addition, all medications (e.g., prescription drugs, over-the-counter drugs, vaccines, herbal or homeopathic remedies, nutritional supplements) used by the patient in addition to protocol-mandated treatment within 7 days prior to initiation of study treatment will be recorded. At the time of each follow-up physical examination, an interval medical history should be obtained and any changes in medications and allergies should be recorded.

Demographic data will include age, sex, and self-reported race/ethnicity.

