## **2. OBJECTIVES AND ENDPOINTS**

### **2.1 PRIMARY OBJECTIVE(S)**

This study seeks to demonstrate that the laboratory can mitigate respiratory virus transmission in underserved populations by using laboratory data to identify communities at risk for increase vial activity (hot spots) and intervening with a test-to-treat model provides increased access to influenza diagnostics and treatment in vulnerable and underserved communities.

1. The hot-spot frequency and hot spot score trend will be measured for each census tract to determine if the screen and treat intervention has an impact on reducing hot spot identification or hot spot score.
  - a. Following each mobile intervention, we will evaluate the hot spot score for the census tracts receiving a mobile screen and treat intervention and SVI-matched census tract not receiving an intervention for 14-days following the screen and treat intervention.
  - b. Patients will receive a follow-up phone call 14-days following their initial screening visit to assess patient and household symptoms and the socioeconomic impact of their test result and treatment access.

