All subjects eligible for Xofluza will receive patient education and counseling on drug information, adherence, side effects, and other patient educational materials, as appropriate. All subjects eligible for influenza antiviral therapy, but having contraindications to the therapy, or do not wish to use the therapy will be referred to their primary care provider, provider, or clinic for further evaluation.

Subjects testing positive for SARS-CoV-2 will be preferred by the pharmacist to the subjects' primary care provider, provider, or clinic for further medical assessment and follow-up, if appropriate. Subjects testing negative for all targets (SARS-CoV-2 and Influenza A&B) with a high index of suspicion for influenza, will be referred by the pharmacist to the subjects' primary care provider, provider, or clinic for further medical assessment and follow-up, if appropriate. All subjects will receive a follow-up call 14-days following the study visit to assess their symptom resolution and the impact of their illness on their well-being (Appendix 1).

The mobile testing unit will be deployed a minimum of 2 times per week following the determination of the influenza season by the New Mexico Department of Health. We expect to screen 50-100 patients per week for the duration of the influenza season (approximately 12 weeks) for a total of 600-1,2000 patients. With an anticipated 10% positivity rate for influenza, we expect at least 5-10 patients per week to be eligible for treatment for a total of 60-120 subjects eligible over the course of the study. All subjects will be provided a survey to evaluated their ability to access respiratory virus testing and their acceptance of and trust in using a mobile unit for access to treatment and therapeutics. Patients positive for SARS-CoV-2 will be counseled on options for treatment and follow up for COVID-19 infection. All subjects enrolled in the study will receive a follow-up phone call 14-days following the initial screening visit.

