### **3.2 END OF STUDY AND LENGTH OF STUDY**

The end of this study is defined as the date when 12 weeks of mobile testing and treating deployment has concluded or the end of “influenza season” as defined by the New Mexico Department of Health, whichever is last. As this is a single dose observational study, there are no follow-up visits scheduled as part of the study. All subjects receiving the therapeutic will receive a follow-up phone call 24-48 hours following administration of Xofluza. All enrolled subjects will receive a follow-up phone call 14-days following the initial screening visit to assess symptom resolution and socioeconomic impact of their test result. The end of the study is expected to occur 12 months after the last patient is enrolled to allow for complete data analysis and evaluation. In addition, the Investigator may decide to terminate the study at any time.

The total length of the study, from screening of the first patient to the end of the study, is expected to be approximately 15 months.

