#### VISIT COMPLETION

Survey returned: \_\_\_ YES \_\_\_ No

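### Treatment obtained after the mobile visit has no working collection point, so objective 1b can describe treatment access only as on-site prescription or referral

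*Combined protocol and SAP*

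**What the plan says.** Section 4.5.2 sets a baseline window: medications used "within 7 days prior to initiation of study treatment will be recorded". For anything later it says: "At the time of each follow-up physical examination, an interval medical history should be obtained and any changes in medications and allergies should be recorded". Section 3.2 states that "there are no follow-up visits scheduled as part of the study" and provides two telephone contacts instead: one at 24-48 hours for those who took the drug, and one at 14 days for everyone enrolled.

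Section 4.4 has a separate rule. It defines concomitant therapy as any medication "used by a patient in addition to protocol-mandated treatment from 7 days prior to the study visit", gives no closing date, and requires it to be reported to the investigator and entered in the patient's medical records.

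Objective 1b, under the primary objective in Section 2.1, gives the 14-day call the task "to assess patient and household symptoms and the socioeconomic impact of their test result and treatment access".

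Section 3.1 sends several groups elsewhere for care. Influenza-positive subjects who have a contraindication or "do not wish to use the therapy will be referred to their primary care provider, provider, or clinic for further evaluation". SARS-CoV-2 positives and test-negative subjects with a high suspicion of influenza are also referred. Section 6.1 repeats that COVID-19 positives are referred to other treatment locations.

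**The concern.** The one timed instruction for updating medications depends on an examination that the study does not hold. If nothing else collects the information, the data cannot separate a referred subject who obtained an antiviral from one who obtained none. For referred subjects that distinction is a central part of what treatment access means, and 1b names treatment access.

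Two further uses depend on the same information. Section 4.4.3 prohibits other influenza antivirals, and compliance after dosing has no defined check. Section 5.3.2 asks investigators to weigh concomitant therapies when judging causality of adverse events. Section 5.3.1 runs the reporting period up to 14 days after dosing, yet no contact is assigned to ask about medication during that time.

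**Working it through.** The point rests on no power or alpha figure. The check is a comparison of the text, followed by arithmetic for scale only.

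**Can any described contact or form capture post-visit treatment?**

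- *Follow-up examination (4.5.2):* would capture it, but none is scheduled (3.2).
- *Open-ended rule (4.4):* would cover it in principle. It names the patient's medical records as the place of entry and gives no time or person for asking after the visit.
- *24-48 hour call (3.1, 3.2):* reaches treated patients only. Its described content is evaluation of signs and symptoms, with referral where needed. No medication question is stated.
- *Case report form (Appendix 1):* has boxes for a prescription given and for referral. It records what happened at the unit, not what followed a referral.
- *Access survey (2.2, Appendix 1):* concerns experience at the mobile unit and is logged at visit completion ("Survey returned"), before a referral could be acted on. Its questions are not reproduced.
- *14-day form (Appendix 1):* asks about household positives and symptoms, dates of symptom resolution and missed activities. It has no item on treatment or medication.
- *Household antivirals:* both 4.4 and 4.5.2 concern the patient, so neither covers household members. Section 1.2 notes that the drug is approved for post-exposure prophylaxis, so household use is plausible.

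**Scale, from the Section 6.1 table** (600-1,200 enrolled, 10-20% influenza-positive, 90% within the window)

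Treated on site = enrolled × positivity × 0.90.

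- Low end: 600 × 0.10 × 0.90 = 54, which matches the table.
- High end: 1,200 × 0.20 × 0.90 = 216. The table prints 180, which does not follow from its own row.

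Not treated on site = enrolled − treated:

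- 10% positivity: 600 − 54 = 546, and 1,200 − 108 = 1,092. Both are 91%.
- 20% positivity: 600 − 108 = 492, and 1,200 − 216 = 984. Both are 82%.
- With the printed 180: 1,200 − 180 = 1,020, or 85%, so that discrepancy does not matter here.

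Influenza-positive but outside the window: 60 − 54 = 6, up to 240 − 216 = 24. No rate is given for declining or for contraindications.

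COVID-19 referrals, by assumption: the Section 6.1 text expects 20-50 COVID-19 positives per deployment of 200-250, that is 20/200 = 10% to 50/250 = 20%. Carried over to the table's enrolment this gives 600 × 0.10 = 60 to 1,200 × 0.20 = 240. The deployment size in that text does not agree with the table's 50-100, so this range shows scale only.

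**The case against.** The strongest reply is that the protocol already requires the information. Section 4.4 has no end date and does not depend on an examination, so a reader who inferred from 4.5.2 that later medication is never captured, or that 4.5.2 is the sole rule, would be wrong. This part of the reply stands. The gap is in carrying out the rule: no described contact or printed form does so after the visit.

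The reply also holds that 1b is not left empty. On-site prescription and referral are on the case report form, and the 14-day form records missed work, school and other activities. That too stands. The documents do not support saying that treatment access cannot be assessed at all; what cannot be described is access beyond the mobile unit.

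A reader might further infer that symptom or household outcomes can no longer be attributed to treatment, or that a comparison of treated with referred subjects is diluted. The plan contains no such comparison. Section 4.2 assigns everyone to the treatment group, Section 6.2 excludes individual efficacy, and Section 6.5 analyses census-tract scores. Nothing in the documents gives a rate of antiviral use elsewhere from which to size a dilution. A medication item would not make attribution possible either, because people who decline or are referred differ from those treated.

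Finally, the Appendix 1 flowchart and the survey questions are not visible in the text reviewed. The 14-day form also refers to symptoms above it although the list follows, so its layout may be disturbed. A treatment question could exist in material not seen. This limits certainty, but it does not resolve the conflict between 4.5.2 and 3.2.

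**Conclusion.** The concern holds as a data-collection gap. Sections 4.5.2 and 3.2 contradict each other, Section 4.4 is not put into practice after the visit, and treatment obtained elsewhere by referred subjects is not systematically captured. Post-dose use of prohibited antivirals and concomitant medication for causality assessment share the gap.

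The 82% to 91% without on-site study drug is an upper bound on the subjects affected. It includes test-negative subjects who are not referred, and it takes every in-window positive as treated. The 60-240 COVID-19 referrals rest on the assumption shown above. The census-tract outcome in objective 1a is untouched. The change is still worth making before the first deployment, because treatment not asked about during the calls would be hard to recover later.

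**What to change.** - Reconcile Sections 4.4, 4.5.2 and 3.2: replace the follow-up examination as the occasion for recording medication changes with the existing 24-48 hour and 14-day calls, and give the 4.4 rule a stated end.
- Add to the 14-day form one item asking whether, since the visit, the subject saw a provider and took any antiviral for influenza or COVID-19 (which, when, where). Add one yes/no item on antiviral use by household members.
- Report objective 1b descriptively by where treatment was obtained (mobile unit, elsewhere, none), and state that no causal comparison is intended.

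No new contact is needed and no clinical rule changes. The cost is a slightly longer call, and the answers will be self-reported.

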#### **4.5.3 Physical Examinations**

A limited, symptom-directed physical examinations will be performed to assess symptoms of influenza-like-illness (cough, sore throat, nasal congestion, headache, feverishness or chills, muscle or joint pain, fatigue).

#### **4.5.4 Vital Signs**

Vital signs will include measurements of weight, respiratory rate, pulse rate, and systolic and diastolic blood pressure, oxygen saturation rate and temperature.

Vital signs should be measured within 60 minutes prior to each Xofluza treatment.

#### **4.5.5 Rapid Influenza Diagnostic Test**

For patients to be eligible for this study, RT-PCR is required to be performed to inform a diagnosis of influenza.

#### **4.5.6 Laboratory, Biomarker, and Other Biological Samples**

For sampling procedures, storage conditions, and shipment instructions, see the laboratory manual.

Unless the patient gives specific consent for his or her leftover samples to be stored for optional exploratory research (see Section 4.5.), biological samples will be destroyed when the final Clinical Study Report has been completed, with the following exception:

- Self-collected nasal swab samples collected for influenza testing may be required to be accessible to the New Mexico Department of Health (NMDOH) for serotyping or other analysis performed for routine influenza

surveillance. If not required for the NMDOH will be destroyed no later than 1 year after the closure of the study or earlier depending on local regulations.

When a patient withdraws from the study, samples collected prior to the date of withdrawal may still be analyzed, unless the patient specifically requests that the samples be destroyed or local laws require destruction of the samples.

However, if samples have been tested prior to withdrawal, results from those tests will remain as part of the overall research data.

Data arising from sample analysis will be subject to the confidentiality standards described in Section 8.4.

#### **4.6 TREATMENT, PATIENT, AND STUDY DISCONTINUATION**

Patients must permanently discontinue study treatment (Xofluza) if they experience any of the following:

- Intolerable toxicity related to study treatment, including development of an immune-mediated adverse event determined by the investigator to be unacceptable given the individual patient's potential response to therapy and severity of the event
- Any medical condition that may jeopardize the patient's safety if he or she continues study treatment
- Investigator determines it is in the best interest of the patient
- Pregnancy
- Anaphylaxis or other severe hypersensitivity reaction
- Loss of clinical benefit as determined by the investigator after an integrated assessment of clinical status (e.g., symptomatic deterioration such as pain secondary to disease) (see Section 3.1.1 for details)

The primary reason for study treatment discontinuation should be documented in the patient's medical records. Patients who discontinue study treatment prematurely will not be replaced.

##### **4.6.1 Patient Discontinuation from Study**

Patients have the right to voluntarily withdraw from the study at any time for any reason. In addition, the investigator has the right to withdraw a patient from the study at any time. Reasons for withdrawal from the study may include, but are not limited to, the following:

- Withdrawal of consent
- Study termination or site closure
- Patient non-compliance, defined as failure to comply with protocol requirements as determined by the Investigator

Every effort should be made to obtain information on patients who withdraw from the study. The primary reason for withdrawal from the study should be documented in the patient's medical records. If a patient requests to be withdrawn from the study, this request must be documented in the source documents and signed by the investigator. Patients who withdraw from the study will be replaced.

If a patient withdraws from the study, the study staff may use a public information source (e.g., county records) to obtain information about survival status.

#### **4.6.2 Study Discontinuation**

The Investigator has the right to terminate this study at any time. Reasons for terminating the study may include, but are not limited to, the following:

- The incidence or severity of adverse events in this or other studies indicates a potential health hazard to patients
- Patient enrollment is unsatisfactory

### **5. ASSESSMENT OF SAFETY**

#### **5.1 SAFETY PLAN**

The safety and efficacy of Xofluza has been investigated in otherwise healthy adult and adolescent populations as well as adult and adolescent patients at high risk of influenza-related complications. Xofluza has been approved in several countries, including Japan and the United States. The safety plan for patients in this study is based on clinical experience with Xofluza in completed and ongoing studies, as well as analysis of cumulative adverse events reporting from post-marketing surveillance. Please refer to the Xofluza Investigator's Brochure for a complete summary of safety information.

Several measures will be taken to ensure the safety of patients participating in this study. Eligibility criteria have been designed to exclude patients at higher risk for toxicities. Patients will undergo safety monitoring during the study, including assessment of the nature, frequency, and severity of adverse events. In addition, guidelines for managing adverse events, including criteria for treatment interruption or discontinuation, are provided below.

#### **5.1.1 Potential Risks Associated with Xofluza**

Xofluza is generally well tolerated, and no important identified or potential safety concerns associated with Xofluza have been identified from clinical studies conducted, to date.

### **5.1.1.1 Hypersensitivity**

Hypersensitivity reactions have been observed in the post-marketing setting which include reports of anaphylaxis/anaphylactic reactions and less severe forms of hypersensitivity reactions including angioedema, and urticaria.

Exclusion criteria for patients with known hypersensitivity to Xofluza or the drug product excipients are included in this protocol, as re-exposure must be avoided.

